9.2 SAMPLE SIZE DETERMINATION

Power analysis was performed based second outcome, TUG score, rather than feasibility outcome due to clinical significance of the former for both mobility and fall risk that is felt to be an important justification for this intervention as a pilot study, whereas feasibility ascertainment does not justify the study but merely indicates lack of existing clinical use of this ketogenic diet protocol.

Abbreviated Title: Tolerability and efficacy of ketogenic diet in Parkinson's Disease

Version Date: 04/19/2021

Considering range of TUG tests reported in Parkinson's Disease off dopaminergic medication of 8-17s (Foreman 2011), mean of 10-15s with SD 2.15-3.7s (Foreman 2011, Brusse 2005, Dal Bello-Haas 2011), and association of 1s increase in TUG time with 5.4% increase in odds of reporting a fall (Nocera 2013), it is suggested that fall rate can be reduced by 20% with a 4s reduction in TUG time, which is therefore considered to be a clinically meaningful difference. Minimal detectable change is reported as 4.85s (Dal Bello-Haas 2011) and 3.5s (Huang 2011).

Based on these studies, the difference of 4.5s between the group means, which was considered as clinically important, and standard deviation (SD) of 4s (or effect size of 1.125) were used for power analysis. A two-sample t-test was applied to estimate sample size by assuming that the primary outcome, TUG, followed normal distributions, and the variances of the two groups were equal. Power analysis indicated that a total of 28 subjects, 14 per group, will be needed to achieve a power of 80% to detect the difference of 4.5s at significant level of 0.0492. The sample size calculation considered one planned interim analysis scheduled to be conducted when 8 subjects per group have completed. Using O'Brien-Fleming approach, the interim analysis will be conducted with bound, $p=0.0054$ ($t\text{-value}=3.287$, $df=16$) and final analysis with bound $p=0.0492$ ($t\text{-value}=2.06$, $df=26$). By anticipating 10% dropout rate, we will need to recruit a total of 32 subjects (16 per group).

Randomization

Stratified randomization method will be used to control the covariates of age (≤ 65 vs. >65) and TUG baseline score (≥ 11.5 s, vs. <11.5 s Nocera 2013). With these two covariates, there are 4 possible block combinations (TUG ≤ 11.5 s & age ≤ 65 , TUG ≤ 11.5 s & age >65 , TUG >11.5 s and age ≤ 65 , TUG >11.5 s & age >65).

9.3 POPULATIONS FOR ANALYSES

32 subjects randomized to either ketosis diet or a low fat (standard American) diet

9.4 STATISTICAL ANALYSES

9.4.1 Analysis of the Primary Endpoint

Descriptive statistical analysis will be performed to assess the feasibility.

9.4.2 Analysis of Secondary Endpoint

To evaluate the diet effect on the TUG score, analysis of covariance (ANCOVA) will be performed with age and TUG score at day 1 as covariates, and TUG score on day 7 as a dependent variable.

Repeated measures ANCOVA with age as a covariate will also be performed to evaluate the within-subject effect: baseline day 1 vs. day 7 (inpatient) vs. 3 weeks (outpatient) of the intervention, and between subject-effect (diet): ketogenic diet vs. standard American diet.

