- Outcomes:** The primary outcome is feasibility, as determined by a composite outcome of recruitment and retention, acceptability and adherence, including full recruitment to study target of 32 participants; completion rate >80% in both inpatient 1-week and outpatient 2-week segments; adherence in the outpatient segment of estimated low carbohydrate diet <10% mean total

Abbreviated Title: Feasibility and efficacy of ketogenic diet in Parkinson's Disease

Version Date: 04/19/2021

daily energy defined as net carbs); and acceptability defined via exit survey (week 3) 4-point Likert efficacy and likelihood scales on how effective ketogenic diet appears on symptoms and how likely ketogenic diet, with or without MCT oil, participants estimate they will continue the diet on at least an intermittent basis in the future.

The secondary outcome is Timed up & go (TUG) mean difference between groups at the end of admission (day 7).

Exploratory outcomes include both group comparisons (mean difference) at day 7 and repeated measures days 1-7 between MCT-KD and SAD groups (in most but not all outcomes; refer to section 1.3 Schedule of Activities for details) and at week 3, when both groups combine to a single ketogenic diet group, and within-group pre vs. post intervention comparisons at 1 & 3 weeks for both groups separately (SAD at 0 & 2 weeks of ketogenic diet vs. MCT-KD group at 1 & 3 weeks, respectively) and all participants, in the following: Stroop word-color interference latency (executive function), n-back recall task (attention and working memory), finger tap speed and rhythm (MN and PQ keyboard tasks), accelerometry amplitude for tremor analysis; 9-hole pegboard test (9-HPT) (daily), heart rate variability HF power, total power (resting, daily), cardiovagal testing via deep breathing and Valsalva Maneuver (pre vs. post), mean subjective on vs. off time (pre vs. post), non-motor severity score (NMSS) pre vs. post, keto-induction symptoms, UPDRS (pre vs. post), EEG spectral power by frequency and connectivity analysis (day 1 vs. day 7 vs. week 3), Geriatric Depression Scale (GDS, pre vs. post)

Study Population:

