2 INTRODUCTION

2.1 STUDY RATIONALE

Three pilot studies of evaluating use of the traditional ketogenic diet in PD have been reported. They showed either reduction in UPDRS, particularly non motor greater than motor scores (Van Itallie 2005, Phillips 2018), or improved cognition (Krikorian 2019). These studies all had limitations, in part related to pilot outpatient design, with gaps or deficiencies identified in the following: monitoring for adherence and reliability of the intervention; degree of ketosis attained; frequency of testing for ketosis; frequency of outcome assessment to obtain adequate signal : noise ratio with respect to biological fluctuations in the disease; reliability of UPDRS rating scale used as primary outcome for small cohort groups; lack of quantitative testing of cognitive and motor functions in the same cohort for comparison; lack of testing for disease mechanism engaged that might account for the proposed benefits.

VanItallie et al reported results of an unblinded, at-home ketogenic diet for 28 days in terms of pre vs. post UPDRS scores of 5 individuals with PD (from 7 with 2 dropouts), 4/5 with Hoehn & Yahr stage 3, who had varying degrees of ketosis mostly high therapeutic range of beta-OHB levels reported (4.8 – 8.9 mM) and one outlier range 1.13 – 1.56 mM). All five participants had decline in total UPDRS score, mostly (4/5 participants) being 21-46% from baseline. There were clear study limitations of placebo effect in study lacking a control group; lack of rater blinding and placebo control; lack of reliable ketosis monitoring aside from infrequent (unreported frequency) serum betaOHB, whereas daily ketone measurement was only urine dipstick and therefore qualitative; lack of monitoring of the diet relying primarily upon self-report via telephone and intermittent patient visits to the dietician; limited study size, and strict 4:1 standard ketogenic diet regimen with 2 drop outs of 7 participants and additional 2/5 remaining participants with reported dietary relapse.

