4. STUDY DESIGN

4.1 OVERALL DESIGN

The experiment will take place predominantly in the Metabolic Unit, 7SW-S (1-week inpatient) and at home (2 weeks outpatient). Additionally, EEG, TUG, and heart rate variability tests will be performed in the HMCS labs within the 7SW-Neurotesting area.

This study is a single center (NIH Clinical Center), phase 1 feasibility/tolerability assessment of MCT oil subtype of ketogenic diet in a PD cohort, randomized, double-blinded vs. standard American (high-carbohydrate) diet based on macronutrient percentages of calculated daily energy expenditure using measured pCO₂ and pO₂ and Weir formula for indirect calorimetry, performed on screening visit, to give caloric macronutrient ratios 50-55% carb, 35% lipid, 10-15% protein in SAD group and 5-10% carb, 80% lipid, 10-15% protein in MCT-KD group on the 7SW-S Metabolic Unit with assistance of CC Nutrition Department staff. Consent, baseline lipid panel, BMP, and pregnancy test will be done at screening visit. Randomization will occur upon screening visit, stratified by age ≥ 65 or < 65 and baseline TUG score ≥ 11.5 s or < 11.5 s. Protein macronutrient percentage of individual calculated daily energy intake will be the same between the two groups. Diet will be within subject factor for both groups, as pre-diet intervention baseline testing is planned for hospital day #1. The potential confound of changes in activity/exercise level while in the hospital on physiologic and clinical outcomes is recognized. To address this, study investigators will form an individualized exercise plan incorporating baseline exercise and activity levels to involve stationary bike at target HR based on age-adjusted HR max target using Tanaka's formula validated in the elderly population, $208 - 0.7 \times \text{age}$, in order to approximate each participant's daily baseline intensity levels from questionnaires.

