(rsEEG + HRV maneuvers) *(day 1, 7, wk 3 only)	30 min*	~1:20
9HPT	10 min	~1:20 (1:50*)
MN / PQ tests	8 min	~1:30 (2 hr*)
SRT / CRT	8 min	~1:38 (2:08*)
Stroop test	8 min	~1:46 (2:16*)
(3) n-back test	8 min	~1:54 (2:24*)
HRV daily	8 min	~2:02 (2:32)*
UPDRS-3	10 min	~2:10 (2:40*)

Abbreviations:
levodopa (L-DA),
dopamine agonist (DA),
Timed Up & Go (TUG),
9-hole pegboard test
(9HPT), simple / complex
reaction times (SRT/CRT),
heart rate variability (HRV)

1:30 - 1:45 total + 30-60 min
(breakfast) → up to 3 hr total
time from last dose

Note: The times listed on the chart are the target timepoints, and while every effort will be made to keep testing as close to the target time as possible, it is expected that there will be some variation in actual testing times. Times will be recorded. Variation in testing times is expected and will not be considered a protocol deviation. Home dose of dopaminergic medications will be given in the morning of the testing in the fasted state approximately 30 minutes prior to breakfast, allowing for at least 1 hour after dose prior to the start of testing to decrease variability in absorption.

Mobility assessment: Timed Up & Go (TUG) test

Abbreviated Title: Tolerability and efficacy of ketogenic diet in Parkinson's Disease

Version Date: 04/19/2021

To test the hypothesis of improvement occurring acutely (within days of reaching ketosis) due to improved mitochondrial function and neurotransmitter signaling, TUG will be tested by AI between group mean difference on study day 7 to target TUG power analysis (see section 9 for details). Pre-intervention screening visit time ≥ 11.5 s or < 11.5 s will be used as covariate for group randomization. Power analysis was chosen for TUG as a measure showing good intra-rater reliability (Dal Bello-Haas et al, 2011) and correlated with fall risk (Nocera et al 2013), hence meaningful for motor function. TUG will be done in the hallway of 7SW Neuro testing with distance of 10 ft demarcated by tape, using chair and stopwatch, best of three trials, daily as per table 2 testing schedule above. To control for biological / Levodopa variability, all secondary/exploratory tests will be done at approximately the same time with respect to dopaminergic Parkinson medication and other psychotropic medication dose and at approximate same time of day and same order of tests. Additionally, plasma levodopa will be measured twice daily at the times defined for BOHB blood draw.

[figure not shown]

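### The day-7 TUG ANCOVA leaves out the screening TUG, which is already collected and used for stratification; adding it is a cheap, modest precision gain

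*Combined protocol and SAP*

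**What the plan says.** Section 4.1 sets the order of events: "Randomization will occur upon screening visit", stratified by age and by TUG at a cut of 11.5 s. Under the mobility assessment it confirms that the TUG in question is the screening-visit one: "Pre-intervention screening visit time ≥ 11.5 s or < 11.5 s will be used as covariate for group randomization".

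The analysis in Section 9.4.2 uses a different TUG reading. For the day-7 outcome, "analysis of covariance (ANCOVA) will be performed with age and TUG score at day 1 as covariates". Day 1 is the first inpatient day, after randomisation but before the diet starts on day 2. Screening TUG does not appear.

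The schedule in Section 1.3 marks TUG at screening, on each of days 1 to 7, and at week 3. Section 9.4.2 also plans a repeated-measures ANCOVA on day 1, day 7 and week 3. Section 8.2 plans a repeated-measures ANOVA of TUG over time without naming the days. The defined secondary endpoint throughout is the between-group mean difference on day 7.

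For session-to-session noise, Section 9.2 offers two published figures: "Minimal detectable change is reported as 4.85s" in one source and 3.5 s in another.

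**The concern.** A single TUG session is a noisy measure of a person's usual mobility. Two pre-diet readings predict day 7 better than one, and the second already exists for every randomised participant. Section 2.1 faults earlier ketogenic trials on "frequency of outcome assessment to obtain adequate signal : noise ratio", so the plan itself treats this kind of noise as a problem.

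What is at stake is precision. Section 1.1 gives effect size and time course as the question to be answered before a larger study. With about 14 per arm, the width of the interval around the diet difference decides how useful that answer is.

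**Working it through.** **The plan's own figure.** Inputs from Section 9.2: difference 4.5 s, SD 4 s, alpha 0.0492 (two-sided, from the hypotheses in 9.1), two-sample t-test. Power is 78.4% at 13 per group and 81.5% at 14, so 14 per group is right. With 10% dropout, 28/0.9 = 31.1, rounded up to 32. The figure reproduces, and it takes no credit for any covariate.

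**What the planned ANCOVA already gains.** The documents state no between-session correlation; take 0.8 as an assumption. Residual SD = 4 × √(1 − 0.8²) = 2.4 s. SE = 2.4 × √(2/14) = 0.91 s. Power for 4.5 s is then 99.7%.

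**Session noise.** Assume that both minimal detectable changes (MDC) are 95% values; Section 9.2 gives no confidence level. Then SEM = MDC/(1.96 × √2):
- 3.5/2.772 = 1.26 s
- 4.85/2.772 = 1.75 s

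**Adding screening TUG.** Let s = SD² − SEM² be the stable between-person variance, with session errors independent (assumed).
- Residual variance with day 1 only: SD² − s²/SD²
- Residual variance with day 1 and screening: SD² − s²/(s + SEM²/2)

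The extra covariate must be paid for. With p normally distributed covariates and N = 28, the variance of the diet difference is inflated by (N − 3)/(N − 3 − p). Going from two covariates (age, day-1 TUG) to three multiplies it by (25/22)/(25/23) = 23/22 = 1.045.

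| SD (s) | SEM (s) | Day 1 only | Plus screening | Cut before cost | Cut after cost |
|---|---|---|---|---|---|
| 4 | 1.26 | 3.03 | 2.35 | 22% | 19% |
| 4 | 1.75 | 5.54 | 4.43 | 20% | 16% |
| 2.15 | 1.26 | 2.64 | 2.23 | 16% | 12% |
| 2.15 | 1.75 | 4.10 | 3.83 | 6% | 2% |

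Simulation at 14 per arm with age in the model gives about 2-18%, in line with the last column. The bottom row combines the smallest SD with the largest noise figure from separate sources. It implies a reliability of only 1.56/4.62 = 0.34, so it is a pessimistic corner.

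**If correlation fades with time.** The table treats the screening reading as being as close to day 7 as the day-1 reading is. Under a set of assumed covariances that decay with time, the cut from adding screening TUG is about 0-11% before cost. Applying 23/22, the best of these (ratio 0.891) becomes 0.93, a cut of about 7%. The worst (ratio 1.0) becomes 1.045, a loss of about 5%.

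**The optional days 5-7 mean.** Residual variance = (s + SEM²/3) − s²/SD².
- SD 4, SEM 1.26: 1.97 against 3.03, so residual SD falls by 19%.
- SD 2.15, SEM 1.75: 2.05 against 4.10, so it falls by 29%.

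These need an effect that is stable over days 5 to 7. For a 2 s effect at correlation 0.8, power is 56% on day 7 and 76% for the days 5-7 mean if the effect is stable. If the effect rises in a straight line from 0 on day 2 to 2 s on day 7, the days 5-7 mean estimates (1.2 + 1.6 + 2.0)/3 = 1.6 s. Power is then 57% against 56%, essentially no gain. Averaging days 2-7 under that rise drops power to 30%.

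**The case against.** The strongest reply is that nothing promised is in danger. Power was computed without covariates, and the planned ANCOVA already does better. Day-1 TUG is a continuous, dose-timed, pre-diet measure of the same quantity as the stratifier, and age is in the model too. All of this stands. A reader might infer that the analysis fails to respect the randomisation, or that the trial is underpowered. The documents support neither.

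The second reply is that the screening reading is the weaker baseline. It is taken at least a week before admission, it lies outside the fixed medication timing described for days 1-7 and week 3, and it is the participant's first TUG in the study, a test on which Section 4.2 expects some learning. This also stands, and is why the range runs down to zero.

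Three further inferences are tempting and go too far.
- **That the other models need the same term.** In the repeated-measures ANCOVA, day 1 is already one of the repeated levels. A screening-TUG main effect leaves the diet-by-time contrast unchanged. For the exploratory ANCOVAs in 9.4.3, no gain from a TUG term has been shown.
- **That six on-diet sessions are thrown away.** The day-2 TUG falls before or just after the first study meal, and Section 4.1 expects ketosis on day 3. Days 3-7 are the five clearly on-diet sessions, and the repeated-measures ANOVA in Section 8.2 may use some of them.
- **That averaging sharpens the day-7 estimate.** It estimates something else. Section 4.1 allows part of the effect to develop over several days, and in that case almost no power is gained.

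**Conclusion.** The omission is real and worth correcting because it costs almost nothing. It is a modest efficiency point, not a flaw in validity or sizing. Adding continuous screening TUG to the day-7 ANCOVA cuts the variance of the diet difference by about 2-18% at 14 per arm after the cost of the covariate. That range assumes 95% minimal detectable changes, SDs of 2.15-4 s, and independent session errors with no fading over time. With fading, the range is about 0-11% before cost, and the low end becomes a small loss after it. The correlation between screening and later TUG is not given in the documents, so the position within these ranges cannot be settled from them.

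**What to change.** In Section 9.4.2, add screening TUG as a continuous covariate to the day-7 ANCOVA, beside age and day-1 TUG, and keep day 7 as the secondary endpoint. Entering it as a continuous value avoids having to settle the stratum boundary, which Section 9.2 writes both as ≥11.5/<11.5 s and as ≤11.5/>11.5 s. State the choice before unblinding, and keep it whatever correlation is seen.

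Optionally, pre-specify the mean of days 5-7, with the same covariates, as a supportive analysis. Label it as a different estimand that gains precision only if the effect is stable over those days.

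On this point, leave the repeated-measures model and the 9.4.3 ANCOVAs as they are.

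The cost is a sentence or two of SAP wording and one degree of freedom, with no new participants, visits or tests.

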Idiopathic Parkinson's Disease of moderate severity, Hoehn & Yahr Stage 2-4, age >50, usual (carbohydrate predominant) diet at baseline. A total of 32 PD patients will be recruited predominantly from the Parkinson's Clinic at NIH and local sites given necessity of three visits to facilitate randomization and baseline data acquisition. Recruitment will continue as per power analysis for Timed Up & Go (TUG).

Phase:	1
Description of Sites/Facilities	Enrollment will occur at Screening Visit, NIH Clinical Center Outpatient Clinic 5 (OP5). Admission will occur at NIH Clinical Center Metabolic Unit, 7SW.
Enrolling Participants:	Unit, 7SW.
Description of Study Intervention:	The study intervention is randomization to MCT-KD (ketogenic diet with 80% energy from lipids including Liquigen® (KetoCal) comprising 25% of the daily lipid energy divided twice daily or typical, standard American diet (SAD) x 6 days, followed by 2 weeks ketogenic diet in both groups at home. The proposed diets are isocaloric and have the same ratio of protein (10-15% daily energy) with similar mealtime boluses to limit differences in L-DOPA absorption. Daily activity and exercise plans will be individualized upon admission including use of stationary bike, aiming to maintain baseline levels. Diet with MCT oil will begin on hospital day 2

[figure not shown]
Abbreviated Title: Feasibility and efficacy of ketogenic diet in Parkinson’s Disease

Version Date: 04/19/2021

and be provided to both groups at outpatient day 1 Both diets will be double-blinded (combination of shakes and similar appearing snacks). MCT-KD will feature reduced carbohydrate intake of 5-10% daily energy requirement calculated in the Metabolic Unit. Safety monitoring will be performed by IMM.

Study Duration: 9 months
Participant Duration: 3 weeks

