The combination of inpatient and outpatient parts of the study involves some degree of discontinuity of the diet, at least in terms of monitoring but also in the diet itself. The latter difference is due to the desire to maintain double-blinding in the inpatient part of the study to minimize placebo effect, while also wanting to assess feasibility of a diet that is thought to be better tolerated than traditional, strict 4:1 (4 grams lipid to 1 gram carb + protein) ketogenic diets. The inpatient diet is predominantly liquid via blended nutrients to facilitate the blinding, but this is not practical to recommend for long-term outpatient therapy. Furthermore, while there is possibility to maintain a control group in the outpatient part of the study, it is felt preferable to prescribe ketogenic diet to all participants outpatient for a few reasons. First, study power will be increased for the key portion of the study: feasibility of MCT-KD in the home. Second, regardless of inpatient randomization group, all participants will have opportunity to try the

Abbreviated Title: Tolerability and efficacy of ketogenic diet in Parkinson's Disease

Version Date: 04/19/2021

ketogenic diet as possible therapy, which should improve study recruitment and limit possible “nocebo” effect that an outpatient control group might otherwise be subject to.

Herein is proposed an inpatient pilot study of MCT ketogenic diet (MCT-KD) compared to standard American diet (SAD) in randomized, double-blind participant groups followed by outpatient study of a similar ketogenic diet with education and meal preparation guidelines, monitored for the inpatient portion with fingerstick beta-OHB levels, continuous glucose monitoring, and respiratory quotient and outpatient via online meal planning app, Diet tracking, correlating with motor physiology, cognitive inhibition and short-term recall, and EEG characteristics to establish which, if any, aspects of known PD test impairments may be modulated by ketogenic intervention in relation to suspected or likely metabolic pathways, to inform subsequent study into symptomatic benefit and/or disease modification.

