that certain medications, medication dosages, or DBS status will interact with dietary composition, either ketogenic or standard at standard protein intake. Study raters will remain blinded to diet group, because randomization scheme will be kept only by biostatistician and intervention status will be known otherwise only by nutrition staff, none of whom are involved in study rating. A possible exception is unblinding due to serious adverse event determined by study PI (non-rater) in consultation with safety monitor in which participant continues in the study, in which case data will be demarcated and not included in statistical analysis. Prior to admission, participants will be instructed to complete a log for 1 week of activities and diet at home. Upon admission to the Metabolic Unit and during hospital day 1, they will continue a regular, healthy hospital diet (carbohydrate predominant) and undergo baseline testing in mobility, physiologic and cognitive measures as per Section 3, Objectives and Endpoints). On hospital days 2-7, they will begin one of two diets: diet A, MCT-KD, according to set macronutrient ratios by daily energy: lipid 80% (25% of which is MCT oil), carb 5-10%, protein 10-15%, expected to be better tolerated than traditional NK, vs. diet B, standard American diet, lipid 30-35%, carb 55%, protein 10-15%. The goal is study time series of betaOHB, respiratory quotient, and continuous glucose ketosis measurements with tests of symptomatic impairment, with the hypothesis that nutritional ketosis augments mitochondrial function within hours of keto-induction and provides further benefit over days due to better functional neurotransmitter supply to key motor and cognitive synapses, aside from any long-term disease modification. Added benefits of an inpatient trial include monitored adherence and a look at biomarkers such as respiratory quotient in the metabolic chamber (CO₂:O₂ expected to go down due to diet), as well as easier access to daily repeated testing such as cognitive focused testing on executive function, memory and learning, as well as quantitative motor assessment of bradykinesia (keyboard, 9-hole pegboard), blinded UPDRS, and pain / fatigue assessment by subjective report.

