Overview of Trial Flow and Events. Figure 1 highlights MCT-KD trial flow and events. We propose a screening enrollment of 1-2 participants per week for total of 32 participants. Upon meeting study criteria and consent, participants are asked to provide one week baseline diet and activity/exercise intake, and then be admitted to NIH CC for a one week study intervention assessing ketosis and symptom outcomes, safety monitoring and potential biomarkers of the diet on Parkinson's EEG and BDNF levels. During admission and discharge, communication will be maintained with participants regarding the requested outpatient portion, in which participants are provided meal plans to continue (or in the case of standard diet participants, begin) a standard ketogenic diet, with MCT oil in the home. The outpatient diet will be given as recommended meals and instructions to be reachable via telephone for twice weekly unscheduled calls from NIH CC Nutrition staff to populate diet adherence using diet tracking linked to study investigator's account. Additionally, study nutritionist / investigator (not involved in study rating) will perform unscheduled twice weekly phone calls to obtain post-screening baseline diet (one week) and outpatient KD intervention adherence assessment (two weeks). Participants will then be asked to return for a follow-up visit in NIH CC OP5 two weeks after discharge date. If the appointment date varies from two weeks for any reason, the same visit and measurements will occur, but visits will be demarcated separately for statistical analysis.

Abbreviated Title: Tolerability and efficacy of ketogenic diet in Parkinson's Disease

Version Date: 04/19/2021

Screening procedure: Following recruitment, potential subjects will be pre-screened by telephone, in person, or via email communication according to the inclusion / exclusion criteria, discussion of the scope of the study and study design, expected potential benefits and side effects. If the potential candidate meets the study eligibility criteria, a screening visit will be scheduled at NIH CC outpatient clinic. The estimated duration of the screening visit is 4 hours, and may be spread over 2 separate days if necessary. Upon registration, an order will be submitted for metabolic tracking (PCO₂:PO₂ gas exchange) for calculation of daily resting energy expenditure.

Informed consent will be obtained prior to any tests or procedures being conducted at the screening visit.

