8.2 EFFICACY ASSESSMENTS

As one of the study aims is to determine feasibility of MCT supplemented ketogenic diet, the efficacy of primary objective of study feasibility as per recruitment, retention, acceptability, and adherence will be determined by a composite outcome, in which all criteria are met: completion rate of both inpatient 1 week and outpatient 2 week segments, with target of >80% for each; recruitment target of 32 participants reached; adherence to outpatient diet with mean daily carb $\leq 10\%$; intervention is acceptable to all participants by Likert scale $\geq 2/4$ of likelihood of using this therapy in the future and effectiveness in symptom reduction.

Efficacy of secondary objective of TUG reduction will be assessed by between-group mean difference at 7 days (MCT-KD vs. SAD). It is presumed that the standard (control) diet will not provide any issues of feasibility. Refer to Section 4.1 Study Design for direct and indirect determinations of ketosis.

Timed Up & Go (TUG)

Efficacy of TUG will also factor effect of time, via repeated measures ANOVA for TUG that will be tested three times per session and fastest time used, with same timing relation to dopaminergic medications.

Efficacy will be tested further in the between group difference between the two diets on outcomes of the following, again with same timing regarding dopaminergic medications:

Exploratory measures will be done as per test schedule in Section 4.1, generally once daily or less.

Stroop Word-Color Interference

this test has been shown to be impaired in PD as part of the executive network of actively choosing the stimulus while inhibiting the background. The latency will be determined from a computer test.

N-Back Task (% correct)

This test (Kirchner, 1958) involves a series of visual stimuli such as letters, and then participants are asked if each stimulus matches a stimulus n trials before. Performance is shown to be impaired in PD to a greater degree than in normal aging

Simple Reaction Time (SRT)

SRT (same cue on computer screen, press button; machine is used already for Chronic Fatigue Syndrome protocol studies and will be made available for the study). PD is consistently shown to have increased latency that is attributed to the akinesia as cardinal motor symptom. The increase in latency is reduced by

Abbreviated Title: Tolerability and efficacy of ketogenic diet in Parkinson's Disease

Version Date: 04/19/2021

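### The supplementary repeated-measures model for TUG names a diet effect that averages three visits, although the arms are assigned different diets at only one of them

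*Combined protocol and SAP*

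**What the plan says.** Section 9.4.2 plans two analyses of TUG.

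- The first is an ANCOVA of day-7 TUG with age and day-1 TUG as covariates. It matches the secondary outcome, which sections 3, 4.1, 8.2 and 9.1 all place at day 7.
- The second is a repeated-measures ANCOVA with age as covariate. Its within-subject and between-subject effects are "baseline day 1 vs. day 7 (inpatient) vs. 3 weeks (outpatient) of the intervention, and between subject-effect (diet): ketogenic diet vs. standard American diet". It names neither an interaction nor a contrast at a given visit. Section 8.2 adds only that a repeated-measures ANOVA will take time into account.

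The assigned diets at the three modelled visits are:

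- **Day 1.** Section 6.1.1 says of all participants that "they will continue a regular, healthy hospital diet (carbohydrate predominant) and undergo baseline testing".
- **Day 7.** The arms are on their randomised inpatient diets.
- **Week 3.** The synopsis has the inpatient diets "followed by 2 weeks ketogenic diet in both groups at home", and describes outcomes "at week 3, when both groups combine to a single ketogenic diet group". Section 4.2 shows that this is deliberate: "it is felt preferable to prescribe ketogenic diet to all participants outpatient for a few reasons".

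**The concern.** In a model with visits as the within-subject factor and arm as the between-subject factor, the between-subject effect is the arm difference averaged over all visits. Here two of the three visits carry no assigned contrast between a ketogenic and a standard diet. The figure that the plan labels as ketogenic versus standard American diet is therefore not the diet difference at the plan's own time point.

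Two things are at stake. If the diet works as assumed, this model could appear to contradict the day-7 ANCOVA merely because it averages. Conversely, an arm difference at week 3, which compares a longer with a shorter ketogenic exposure, could be reported as ketogenic versus standard diet.

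**Working it through.** **Inputs from section 9.2.** Day-7 difference d = 4.5 s, SD 4 s, 14 per arm, final significance level 0.0492.

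**Assumptions, because the documents give no values.** The week-3 arm difference c; the within-person correlation ρ between visits, taken as equal for all pairs and ranging from 0.3 to 0.9. Power below is from the noncentral t at two-sided 0.05; using 0.0492 lowers it by about 0.003 at most.

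**Plan's own figure.** A two-sample t-test with 14 per arm has noncentrality 4.5 / (4 × √(2/14)) = 2.98. With 26 df at 0.0492, power is 81.5% (78.4% with 13 per arm). The stated 14 per arm for 80% power is reproduced.

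**What the named effect estimates, with diet read as randomised arm.** The arm differences at day 1, day 7 and week 3 are 0, d and c, so the effect is (0 + d + c)/3:

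- c = 0: 4.5/3 = 1.5 s
- c = 0.5d: 6.75/3 = 2.25 s
- c = d: 9/3 = 3.0 s

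It would equal d only if c = 2d.

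**Power.** The SD of a three-visit mean is 4 × √((1 + 2ρ)/3). At ρ = 0.3 this is 2.92, with standard error 2.92 × √(2/14) = 1.10 and noncentrality 1.5/1.104 = 1.36 for c = 0. At ρ = 0.9 the values are 3.86, 1.46 and 1.03. The SD of the day-7-minus-day-1 change is 4 × √(2(1 − ρ)): 4.73 at ρ = 0.3 and 1.79 at ρ = 0.9. The day-7 ANCOVA has residual SD 4 × √(1 − ρ²).

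| Quantity | Estimate | ρ = 0.3 | 0.5 | 0.7 | 0.9 |
|---|---|---|---|---|---|
| Three-visit effect, c = 0 (25 df) | 1.5 s | 26% | 22% | 19% | 17% |
| Three-visit effect, c = 0.5d (25 df) | 2.25 s | 50% | 42% | 36% | 32% |
| Three-visit effect, c = d (25 df) | 3.0 s | 74% | 65% | 57% | 51% |
| Day 7 minus day 1, between arms (26 df) | 4.5 s | 68% | 82% | 96% | >99% |
| Day-7 ANCOVA (24 df) | 4.5 s | 85% | 91% | 98% | >99% |

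**Dropping week 3 is not enough.** Over day 1 and day 7 alone the main effect is (0 + 4.5)/2 = 2.25 s, with power 43% to 31%.

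**How often the two planned analyses would part.** In simulation (20,000 trials per setting, age as covariate), the day-7 ANCOVA is significant and the three-visit effect is not in 58–84% of trials if c = 0, and in 17–50% if c = d, over the same range of ρ.

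**If diet is instead coded as eaten at each visit.** With visit effects and the same correlation structure, the generalised least squares coefficient is d − cρ/(1 + ρ). If c = 0 it is 4.5 s at any ρ. If c = d it is 4.5 × (1 − 0.3/1.3) = 3.46 s at ρ = 0.3 and 4.5 × (1 − 0.9/1.9) = 2.37 s at ρ = 0.9. The two codings therefore estimate different quantities.

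**The case against.** The strongest reply is that the plan already assigns the diet question to the day-7 ANCOVA: 9.4.2 introduces that analysis as the evaluation of the diet effect, and the repeated-measures model is an addition that the trial was never powered for. This stands. It limits the reach of the point, and low power in a supportive analysis is not a defect in itself.

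Second, models of this kind are commonly fitted with the interaction, and 9.4.2 does not exclude it. With c = 0, the simulated interaction test has power of about 72%, 86%, 98% and nearly 100% at ρ = 0.3, 0.5, 0.7 and 0.9. But a term that software prints is not a pre-specified estimate, and the only diet test named for this model is the averaged one.

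Third, section 4.1 calls diet a within-subject factor for both groups, which could point to coding by diet eaten. A reader might infer that the dilution to (0 + d + c)/3 occurs under any coding; it does not, as the last calculation shows. Arm is the natural reading of a between-subject effect, but the two sections leave the coding open.

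Fourth, the documents give neither c nor ρ, so the size is conditional. A reader might infer that the effect always shrinks to one third; that holds only if c = 0. Nor does the shared outpatient diet imply c = 0, since the assigned exposures still differ in length.

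**Conclusion.** The point holds for the supplementary model. With diet read as randomised arm, its only named diet test estimates (0 + d + c)/3. Under the plan's values that is 1.5 s with 17–26% power if c = 0, and 3.0 s with 51–74% power if c = d, against 4.5 s for the between-arm change from day 1 to day 7. The averaging follows from the design. The figures rest on the assumed c, on ρ between 0.3 and 0.9, and on equal correlation between visits.

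A reader might infer that the test of the secondary outcome is biased or the trial underpowered. The documents do not support that: the day-7 ANCOVA makes the right comparison, and the sample size is based on the day-7 difference. TUG is also not the primary outcome, which is feasibility. Severity is minor to moderate.

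**What to change.** In 9.4.2:

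1. Define the between-subject factor as randomised arm, and reconcile this with the description of diet in 4.1.
2. Name the arm-by-time contrast (day 7 minus day 1, between arms) as this model's diet estimate, in support of the day-7 ANCOVA.
3. State that the three-visit main effect will not be reported as ketogenic versus standard diet.
4. Report week-3 TUG as within-arm change. The synopsis sets out such comparisons by exposure ("SAD at 0 & 2 weeks of ketogenic diet vs. MCT-KD group at 1 & 3 weeks, respectively"), but lists them for exploratory outcomes, so the plan would have to extend them to TUG.
5. Label any week-3 arm difference, here or in an ANCOVA under 9.4.3, as a comparison of assigned sequences: nominally about 3 versus 2 weeks of ketogenic diet among those who take up the outpatient diet. Sections 6.2.4 and 6.4 leave participants free to decline it.

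The cost is SAP wording only, with no added participants, visits or tests. Claims about week 3 become weaker because they have no concurrent control, which the design already implies.
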